Study Protocol and Statistical Analysis Plan

How Long Should a Behavioral Activation Single-session Intervention be? A Four-armed
Trial Comparing Effectiveness by Intervention Duration

ClinicalTrials.gov ID NCT06313736

April 17, 2024

Protocol

Researchers will use the crowdwork platform CloudResearch Connect to recruit and compensate participants. Researchers will pay participants \$0.25 USD for completing the screener and (if eligible) the study information sheet. If participants are eligible, researchers will send them invites through the crowdwork platform to participate in the next parts of the study. Researchers will pay them \$4.00 for completing session 1 of the study and \$1.00 for the 8-week follow-up. Participants are only allowed to complete the study once and cannot participate in the study if they have participated in another study from the research team relating to depression on CloudResearch Connect in the last two months.

Researchers will recruit a sample of 1,100 adults who struggle with depression. To recruit these adults, potential participants will complete a screener and, if eligible, read the study content information and decide whether to participate (2 minutes). Within five days, participants who consent will be invited to complete the first part of the study. In this part, they will first complete a questionnaire of demographics and well-being at baseline (roughly 4 minutes), be randomly allocated to one of four conditions with equal odds of assignment to each condition, complete the SSI to which they were randomized (2-15 minutes) and then complete the post-test measures (roughly 4 minutes) just after the SSI and eight weeks later. Combined across all three study sessions, the study should take roughly 29 minutes. At the end of the study, researchers will offer participants access to a list of free online mental health support resources (shown in supporting documents). At the end of the study, researchers will also offer participants permanent access to all four SSIs.

The research team created the SSIs of different lengths aiming to make the active elements in each SSI as consistent as possible. Thus, even though the 2-minute version contains less content than the 15-minute version, researchers tried to ensure it expresses the same general message and activates similar mechanisms of change. Participants will complete questionnaires asking about their well-being and experiences with the interventions at baseline, post-test, and 8-week follow-up.

All interventions and survey materials are available at <https://osf.io/g846j>.

Statistical Analysis Plan

Main analysis: The main DV is change in depressive symptoms (PHQ-8) from baseline to 8-week follow-up. The main analysis compares change in PHQ-8 score from baseline to 8-week follow-up across experimental conditions. Researchers will use a mixed-effects model predicting depressive symptoms with condition, measurement time point (1 = baseline, 2= 8-week follow-up), and the 2-way interaction between condition and measurement time point as IVs and a participant identifier as a random intercept. Using the “lme4” package in R, these analyses will take the following form:

`lmer(phq8 ~ time*condition + (1|pid))`

Secondary analysis: Researchers will re-run the same analysis as above separately for each secondary outcome collected. Researchers will also duplicate the main analysis but with the following covariates included in the mixed-effects model: gender (multiple choice), age (continuous), ethnicity (categorical), education level (categorical), employment (categorical), and if one completed the study on a phone (binary).

Inference criteria

For all analyses, researchers will use the standard $p < 0.05$ criterion for determining statistical significance. Researchers will use two-tailed tests for each of researchers' analyses.

Data exclusion

Main analyses will be limited to only those participants who 1) were randomized to a condition (i.e., those who consented to participate and completed the baseline measures), 2) did not indicate that they did not participate seriously at the end of the study, and 3) completed the study only once.

Missing data

Based on researchers' previous work on Cloudresearch Connect, researchers do not foresee a great deal of missing data or differential dropout. Although researchers will take efforts to avoid missing data (e.g., a financial incentive for completing the study and reminder emails), it is not necessary to impute missing data before performing a longitudinal mixed-model analysis (Twisk et al., 2013). Participants with missing data at some assessments will be included in the analysis and results will be modeled on the basis of the available data.

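### Does the plan need a margin rule so that a non-significant difference between intervention lengths can be read as support for a shorter version?

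*Combined protocol and SAP*

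**What the plan says.** The title opens with "How Long Should a Behavioral Activation Single-session Intervention be", and its second half announces a four-arm comparison of how well the versions of different duration work. Under Protocol, 1,100 adults are to be recruited and allocated with equal chance to four conditions. All of them are single-session interventions, lasting 2 to 15 minutes. On how the versions were built, the document concedes that the 2-minute one has less content but adds that "researchers tried to ensure it expresses the same general message and activates similar mechanisms of change".

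The Main analysis states: "The main analysis compares change in PHQ-8 score from baseline to 8-week follow-up across experimental conditions". The model is a random-intercept mixed model for PHQ-8 with time, condition and their interaction. Inference criteria then applies one rule to everything: "researchers will use the standard $p < 0.05$ criterion for determining statistical significance", followed by "Researchers will use two-tailed tests for each of researchers' analyses".

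The document gives no equivalence or non-inferiority margin, confidence-interval rule, reference arm, named joint test or comment on how a non-significant result will be read.

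**The concern.** In many trials a null result simply means that no benefit was shown. Here it bears on the question itself, because a 2-minute version that loses little against a 15-minute one would be a useful answer. A small difference is also plausible, since the versions were meant to work through similar mechanisms. Yet a p-value above 0.05 cannot separate a shorter version that loses little from a trial that could not tell.

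If the authors took a null result as support for the shortest version, the threshold for a negligible loss would have been chosen after seeing the data, and a real deficit could pass as equivalence. The model formula adds to the unease: it does not say that condition is a factor, which term or terms carry the primary test, or which arm is the reference.

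**Working it through.** **Inputs from the document:** 1,100 participants, four equal arms (1,100/4 = 275 per arm), two-tailed 5% test, outcome PHQ-8 change to 8 weeks. The 1,100 comes with no power, effect size or SD, so there is no figure of the plan's own to reproduce.

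**Assumed, not in the document:** PHQ-8 SD 5; correlation between baseline and follow-up (ρ) 0.5 to 0.7; 275 analysed per arm, or 220 after 20% loss; illustrative margins M of 0.75 and 1.25 points.

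**Formulas:**
- Standard error of a pairwise difference in change: SE = SD × √(2(1 − ρ) × 2/n). For ρ = 0.5 and n = 275: 5 × √(2 × 0.5 × 2/275) = 0.426.
- Chance that one pairwise test misses a true loss δ: Φ(1.96 − δ/SE) − Φ(−1.96 − δ/SE).
- Chance that the 95% interval excludes a loss above M when the true loss is δ: Φ((M − δ)/SE − 1.96).

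| n per arm | ρ | SE | 95% half-width | Test misses true 0.75 loss | Equal arm passes, M = 0.75 | Equal arm passes, M = 1.25 | True 0.75 loss passes, M = 1.25 |
|---|---|---|---|---|---|---|---|
| 275 | 0.5 | 0.426 | 0.84 | 58.0% | 42.0% | 83.4% | 21.6% |
| 275 | 0.7 | 0.330 | 0.65 | 37.8% | 62.2% | 96.6% | 32.8% |
| 220 | 0.5 | 0.477 | 0.93 | 65.0% | 34.9% | 74.6% | 18.1% |
| 220 | 0.7 | 0.369 | 0.72 | 47.2% | 52.8% | 92.3% | 27.2% |

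**Does non-significance establish equality?** No. One pairwise test misses a true 0.75-point loss 38 to 65% of the time. The joint 3-df test misses it 36 to 67% of the time if one arm alone is worse.

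**Would a margin rule settle the matter at this size?** Only in part.
- At M = 0.75 an equal arm fails to pass 38 to 65% of the time (100% minus 62.2% and 34.9%). This is the same range as the miss rate, because the same SE drives both. All three shorter arms pass together 13 to 38% of the time.
- At M = 1.25 an equal arm usually passes, but so does an arm 0.75 points worse in 18 to 33% of trials.
- The smallest margin with 80% power per comparison is 2.80 × SE, or 0.93 to 1.34 points over the four rows.
- For M = 0.75 at 80% power, n = 7.85 × 2 × V/0.75², where V = 2(1 − ρ) × 25 is the variance of change. V = 25 gives 698 per arm and V = 15 gives 419, so 1,676 to 2,792 in total against 1,100 recruited.
- These figures carry no multiplicity control. With Holm over three comparisons the average pass rate for equal arms at M = 0.75 falls to 24 to 52%. Ordinary 95% intervals do not implement Holm, so the interval rule and the test rule could disagree.

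**Is the primary test recoverable from the text?** Yes. Comparing change across four named conditions calls for condition as a factor and a joint test of its three interaction terms with time. The choice of reference arm alters neither that joint test nor the model fit, and every pairwise difference with its interval comes from the same model.

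**The case for a change.** The strongest case for a change is this. The trial asks a practical question to which a null result is relevant, and its design makes a small difference plausible. Confidence intervals can be reported anyway, but without a threshold fixed beforehand someone must decide afterwards how small is small enough. Adding a margin costs only wording and contrasts from the same fit. It does discriminate: in simulation, given a non-significant joint test and a 0.75-point margin, an equal arm is called comparable 35 to 63% of the time and an arm truly 0.75 points worse only 3 to 6%.

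Much of this stands. The gap is real and the arithmetic is sound. The 3 to 6% is largely built in, however: when the true loss equals the margin, the rule passes it 2.5% of the time by construction, before conditioning on a null. The 35 to 63% leaves out the multiplicity control that three comparisons would need. Nor would a margin repair the lack of an inactive control. The document describes only active versions, so a shorter arm comparable to the longest could mean that both work or that neither does.

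**Conclusion.** No change to the plan is called for. The plan sets out a two-sided comparison of effectiveness by duration and analyses it with a valid randomised contrast. Its default reading of a non-significant result, that no difference was shown, is correct. Nothing in the document says that a null result favours a shorter version, so the concern guards against a possible misstatement in the report rather than an error in the text. The missing joint test, factor coding and reference arm are details that analysts would fill in the same way.

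A margin rule is a legitimate alternative design choice, but not one that statisticians would accept without debate. The sponsor would have to choose and defend the margin, and on the assumed SD of 5 and correlation of 0.5 to 0.7 the planned size supports only margins of about 0.9 to 1.3 points at 80% power per comparison. A tighter margin would often end in an inconclusive result; a looser one would let through losses of the size used here as an example. A larger SD would make this worse: with SD 6, 220 per arm and correlation 0.5, an equal arm passes a 1.25-point margin 59% of the time and a 0.75-point margin 26%.

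One limit remains for readers of the results: under this plan p ≥ 0.05 cannot support a claim that a shorter version is as good.

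### The primary model compares raw PHQ-8 change between arms; adjusting for the baseline score already collected would be as precise or more precise, at almost no cost

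*Combined protocol and SAP*

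**What the plan says.** The Main analysis section of the SAP defines the outcome: "The main DV is change in depressive symptoms (PHQ-8) from baseline to 8-week follow-up". The model has condition, time (baseline and 8 weeks) and "the 2-way interaction between condition and measurement time point as IVs and a participant identifier as a random intercept"; the R call, with its closing brackets cut here, is "lmer(phq8 ~ time*condition + (1|pid". The Protocol section fixes the order of events: "they will first complete a questionnaire of demographics and well-being at baseline (roughly 4 minutes), be randomly allocated to one of four conditions".

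The Secondary analysis section adds two things. For other outcomes, "Researchers will re-run the same analysis as above separately for each secondary outcome collected". For adjustment, "Researchers will also duplicate the main analysis but with the following covariates included in the mixed-effects model"; the list is gender, age, ethnicity, education, employment and phone use. Baseline PHQ-8 is not on it.

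Under Data exclusion, randomised participants are described as "those who consented to participate and completed the baseline measures". Under Missing data, "researchers do not foresee a great deal of missing data or differential dropout", and participants with missing assessments stay in the mixed model.

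**The concern.** The term `time*condition` contains a condition main effect, which gives each arm a free baseline mean. With two time points and complete data, the interaction then reduces to the difference between arms in mean change. That is the same as adjusting for baseline with the slope fixed at 1 instead of estimated. If the true slope is below 1, change over-corrects for chance baseline differences and adds noise.

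The covariate-adjusted version does not help. It omits baseline PHQ-8, and time-constant covariates entered as main effects leave the interaction unchanged when data are complete.

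Precision matters in this trial because the arms are different lengths of one intervention, built to deliver the same content. Differences between them may be small, and narrower intervals are available without recruiting anyone.

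**Working it through.** **Inputs.** From the documents: 1,100 adults and four equally likely arms, so 1,100/4 = 275 per arm; two-sided 0.05. The documents give no power calculation, SD, correlation, target effect or dropout rate, so there is no stated precision figure to reproduce. Assumed: the same covariance in every arm; baseline to 8-week correlation ρ of 0.5 to 0.8; 8-week/baseline SD ratio k of 1 or 1.25; loss at 8 weeks of 0 or 15%.

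**1. What the planned model estimates.** In one simulated complete data set (4 × 275, ρ = 0.6, k = 1), the REML interaction estimates were −0.16902, 0.00313 and −0.06354, each with SE 0.07578. Ordinary regression of change on arm gave the same values to five decimals. ANCOVA on the same data had SEs of 0.0693 to 0.0694.

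**2. Complete data.** In units of the baseline variance, the variance per participant is

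- change: 1 + k² − 2kρ
- ANCOVA: k²(1 − ρ²)

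The difference is (1 − kρ)², which is never negative and is zero only when the slope kρ equals 1. Example at ρ = 0.6: for k = 1, 1 + 1 − 1.2 = 0.80 against 1 − 0.36 = 0.64, ratio 0.800; for k = 1.25, 1 + 1.5625 − 1.5 = 1.0625 against 1.5625 × 0.64 = 1.000, ratio 0.941.

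The 95% half-width for two arms is 1.96 × √(2V/275) in baseline SDs. The per-arm size at which the planned model would match ANCOVA with 275 is 275 divided by the ratio.

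**3. Random loss.** Let p = 0.85 be the share retained, r = 2kρ/(1 + k²) the working correlation of the random-intercept model, and a = r + (1 − r)p. The per-arm variance times n is

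- plan, using everyone: (k² − 2akρ + a²)/p + (1 − r)²(1 − p)
- ANCOVA, completers only: k²(1 − ρ²)/p

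| k | ρ | Change V | ANCOVA V | Ratio | Half-width, plan → ANCOVA | Plan n per arm to match | Ratio, 15% loss |
|---|---|---|---|---|---|---|---|
| 1 | 0.5 | 1.000 | 0.750 | 0.750 | 0.167 → 0.145 | 367 | 0.779 |
| 1 | 0.6 | 0.800 | 0.640 | 0.800 | 0.150 → 0.134 | 344 | 0.825 |
| 1 | 0.7 | 0.600 | 0.510 | 0.850 | 0.129 → 0.119 | 324 | 0.870 |
| 1 | 0.8 | 0.400 | 0.360 | 0.900 | 0.106 → 0.100 | 306 | 0.914 |
| 1.25 | 0.5 | 1.313 | 1.172 | 0.893 | 0.191 → 0.181 | 308 | 0.905 |
| 1.25 | 0.6 | 1.063 | 1.000 | 0.941 | 0.172 → 0.167 | 292 | 0.946 |
| 1.25 | 0.7 | 0.813 | 0.797 | 0.981 | 0.151 → 0.149 | 280 | 0.977 |
| 1.25 | 0.8 | 0.563 | 0.563 | 1.000 | 0.125 → 0.125 | 275 | 0.987 |

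A simulation with 15% loss (4,000 replicates, REML fit of the planned model) gave ratios of 0.798, 0.842, 0.885, 0.927 for k = 1 and 0.917, 0.954, 0.980, 0.985 for k = 1.25, all within 0.02 of the formula. Type I error was 4.9–5.5% for the plan and 5.0% for ANCOVA.

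**4. Power, for scale.** For an assumed pairwise difference of 0.20 SD with k = 1 and no loss, power rises from 65.0% to 77.3% at ρ = 0.5, from 74.6% to 83.4% at 0.6, from 85.7% to 90.7% at 0.7 and from 96.0% to 97.4% at 0.8.

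**5. Do participants without an 8-week score matter?** An equal-baseline model with an unrestricted 2×2 covariance, fitted to everyone by maximum likelihood, factors into a baseline part and an 8-week-given-baseline part with separate parameters. The arm contrast lies wholly in the second part. Over 20 simulated data sets with dropout (60 contrasts), this model and completers' ANCOVA differed by at most 8e-8.

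**6. Differential dropout.** Suppose ρ = 0.6, k = 1.25, dropout odds doubling per baseline SD in one arm only, and 15% random loss elsewhere (8,000 replicates). With 15% loss in that arm the plan's bias is −0.016 baseline SD (Type I error 5.7%); with 30% loss it is −0.032 (6.9%). ANCOVA's bias is 0.001 in both cases (4.7% and 5.2%). At k = 1 with 15% loss the plan's bias is 0.0009, within simulation error.

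**The case against.** The strongest reply is that nothing is wrong. The plan names change as its outcome, the model estimates change, and under randomisation the test is valid. That stands, and it limits the point to efficiency.

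The gain also rests on quantities the documents do not contain. Screening for depression may narrow the baseline spread, which would push the gain towards the lower rows of the table. Variance reductions also look larger than their effect on intervals: widths fall by 13%, 11%, 8% and 5% at equal SDs, and by 6%, 3%, 1% and 0% at ratio 1.25. All of this stands. It makes the benefit uncertain in size; no cell of the table shows a loss.

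The guarantee needs a common covariance across arms. With slopes of 0.9, 0.9, 0.5 and 0.5 and residual variance 0.5, the pooled slope is 0.7. For the first two arms ANCOVA's variance is 0.5 + 0.2² = 0.54 against 0.5 + 0.1² = 0.51 for change, a ratio of 1.06. This is correct, but the loss is small and such divergence is unlikely among versions of one intervention.

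Completers' ANCOVA also departs from the Missing data section, which keeps participants with missing assessments in the analysis. Step 5 shows that under a common covariance they add no information on this contrast, and a model that retains them is available.

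Finally, the differential-dropout scenario is an assumption, and the plan does not expect such dropout. It is a minor supporting observation, and the recommendation does not depend on it.

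**Conclusion.** The concern holds as a recommended improvement to a valid analysis; it does not correct an error. Baseline PHQ-8 is measured before randomisation and is available for everyone in the analysis set, yet no planned model uses it as a covariate. With complete data the planned interaction is a raw change-score contrast.

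Given a common covariance across arms, ANCOVA is never less precise in large samples. The gain runs from nil to moderate, and where it falls depends on the correlation and the two SDs, which the documents do not give. Random loss of 15% leaves variance reductions of 22% to 9% at equal SDs and 10% to 1% at SD ratio 1.25.

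**What to change.** Name one primary analysis: ANCOVA of 8-week PHQ-8 on condition and baseline PHQ-8, `lm(phq8_8wk ~ condition + phq8_base)`. Using change as the response with the same covariate gives identical condition estimates, so the stated outcome is kept. Add baseline PHQ-8 to the covariate-adjusted version, and treat secondary outcomes measured at baseline in the same way. Keep the planned mixed model as a sensitivity analysis, to which the Missing data statement on including incomplete participants would then apply.

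If the sponsor wants participants without an 8-week score formally in the primary analysis, the one alternative is the equal-baseline model. It needs time recoded as numeric 0/1 (the plan codes it 1/2), no condition main effect, and different variances at the two times. It can be fitted with `gls` in nlme, or in lmer with `(1|pid) + (0+t|pid)` provided 0 ≤ covariance ≤ baseline variance ≤ 8-week variance. It should not be fitted with `(1|pid)` alone, because the standard errors are then wrong when the SDs differ.

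The cost is one line of code and one estimated slope. No new data are needed, and nobody is lost for a missing covariate, because the analysis set requires completed baseline measures.

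### The random-intercept primary model assumes equal PHQ-8 variance at baseline and 8 weeks, so its standard errors may be modestly wrong if follow-ups are missing, and it leaves baseline precision unused

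*Combined protocol and SAP*

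**What the plan says.** The Statistical Analysis Plan (Main analysis) compares PHQ-8 change from baseline to 8 weeks across the four conditions. The model has condition, time and their interaction, with "a participant identifier as a random intercept". The code is "lmer(phq8 ~ time*condition + (1|pid" (closing brackets omitted here). The same model is re-run for each secondary outcome and once more with demographic covariates. No version allows the variance to differ by occasion, and none uses robust standard errors.

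On missing data, the plan does not impute. Participants lacking some assessments stay in, and "results will be modeled on the basis of the available data". It expects little missing data but gives no rate.

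On entry, the Protocol says that "potential participants will complete a screener and, if eligible", they go on to consent. Those who consent are invited within five days to a session that begins with a separate baseline questionnaire. The screening instrument and cut-off are not stated.

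On inference, "researchers will use the standard $p < 0.05$ criterion for determining statistical significance". The tests are two-sided.

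**The concern.** A random intercept plus one residual variance gives compound symmetry: one marginal variance for both occasions and one covariance. With two complete measurements per person this is harmless, because the interaction test is then the comparison of change scores. Once some people have only a baseline, the fitted covariance does real work. It sets the slope by which a missing 8-week score is predicted from baseline, and it sets the standard error. If the true variances differ, both are wrong.

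The direction is not known. Selection at a screener shortly before baseline can narrow the baseline spread more than the spread eight weeks later, which would make the standard errors too small. A spread that shrinks would make them too large. At stake are the p-values and intervals for the comparisons between durations, and for every secondary outcome that reuses the model.

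A second loss does not depend on dropout. The model estimates a free baseline mean in each arm although randomisation makes those means equal in expectation. It therefore behaves as a change-score analysis and does not use the precision that baseline PHQ-8 offers.

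**Working it through.** **Inputs from the documents.** Two-sided alpha is 0.05. The target is 1,100 participants in four equal arms ("be randomly allocated to one of four conditions with equal odds of assignment to each condition"), so 1,100 / 4 = 275 per arm. There are two occasions, and the model is as quoted above. The 1,100 cannot be reproduced, because no effect size, SD, power or dropout rate is given.

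**Assumptions (none is in the documents).** Baseline SD s1, 8-week SD s2, correlation r of 0.5 to 0.6, and dropout d unrelated to arm and outcome. Write p = 1 − d and c = r·s1·s2.

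**Step 1: what the planned model converges to.** Let V be its common variance and b its within-person correlation, which is also its slope for predicting a missing follow-up. In large samples it minimises

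`p·[log(V²(1−b²)) + (s1² + s2² − 2bc)/(V(1−b²))] + d·[log V + s1²/V]`

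**Step 2: variance of one arm's estimated change, times n.**

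- Reported by the model: `V(1−b²)/p + (1−b)²V`
- True: `E/p + (1−b)²s1² − 2(1−b)k`, where `E = s2² − 2bc + b²s1²` and `k = c − b·s1²`

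**Step 3: convert to actual alpha.** Let R be the reported SE divided by the true SE. Pairwise alpha is `2Φ(−1.96R)`. For the 3-df interaction test it is `P(χ²₃ > 7.815R²)`.

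**Check with complete data** (SD 4 to 5.5, r 0.5, so c = 11). V = (16 + 30.25)/2 = 23.125 and b = 11/23.125 = 0.476. Both variances equal 16 + 30.25 − 22 = 24.25, so R = 1 and alpha is 5.0%.

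**Worked case, same SDs, 20% dropout.** V = 22.19 and b = 0.4635, against a true slope of 11/16 = 0.69.

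- Reported: 22.19 × 0.785/0.8 + 0.288 × 22.19 = 21.77 + 6.39 = 28.16
- True: 23.49/0.8 + 0.288 × 16 − 2 × 0.5365 × 3.584 = 29.36 + 4.61 − 3.85 = 30.12
- R = √(28.16/30.12) = 0.967, giving pairwise alpha 5.8% and 3-df alpha 6.3%

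**Results** (pairwise / 3-df alpha; r of 0.5 or 0.6 changes entries by about 0.1 point at most):

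| Assumed SD, baseline to 8 weeks | 10% dropout | 20% | 35% |
|---|---|---|---|
| 4 to 5.5 | 5.4% / 5.6% | 5.8% / 6.3% | 6.6% / 7.6% |
| 4 to 4.6 | 5.2% / 5.3% | 5.4% / 5.5% | 5.7% / 6.0% |
| 5 to 5 | 5.0% / 5.0% | 5.0% / 5.0% | 5.0% / 5.0% |
| 5 to 4 | 4.7% / 4.6% | 4.5% / 4.2% | 4.1% / 3.7% |

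**Simulation check.** For SD 4 to 5.5 and r 0.6 with 4 × 275 participants (10,000 runs, Monte Carlo SE about 0.2 points), the planned model's 3-df alpha was 5.1%, 6.0%, 6.2% and 7.1% at 0%, 10%, 20% and 30% dropout. An unstructured covariance gave 5.2%, 5.4%, 5.5% and 5.1%, close to nominal and with no trend.

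**Precision with complete data, 275 per arm.** The pairwise SE is `√(2·var/275)`. For the change score, var = s1² + s2² − 2c. For the baseline-adjusted comparison, var = s2²(1 − r²).

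- SD 4 to 5.5, r 0.5: √(2 × 24.25/275) = 0.420 against √(2 × 22.69/275) = 0.406
- Equal SD 5, r 0.5: √(2 × 25/275) = 0.426 against √(2 × 18.75/275) = 0.369

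**The case against.** The strongest reply is that nothing in the documents shows this trial has the problem. There is no SD, no cut-off, and no statement that the screener is the PHQ-8. Baseline is measured separately after screening, which weakens any range restriction. Simulated screened samples with assumed cut-offs gave only mild widening, from SD about 4.0 to 4.6 and from 4.6 to 4.9. Their 3-df alpha was 5.1% to 5.2% at 10% dropout and 5.3% to 5.5% at 20% (Monte Carlo SE about 0.35 to 0.4 points), which cannot be told apart from 5%. It reached 6.1% to 6.8% only at 35%. The plan also expects little dropout, from experience on the same platform, with payment and reminder emails in support.

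All of that stands, and it limits the point. A reader might infer that the 5% level is exceeded whenever follow-up is incomplete, or that screening has in fact narrowed the baseline spread. The documents support neither. Equal variances give 5.0% at any dropout rate, and a shrinking spread gives a conservative test.

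It can also be said that change is a legitimate primary outcome, and that the two benefits peak under opposite assumptions: the larger precision gain comes with equal SDs, where the error-rate problem vanishes. That is fair. But the recommended model still estimates between-arm differences in change, and it helps in both situations. The expectation of low dropout carries no figure, and the follow-up comes eight weeks later for a $1.00 payment. The argument against imputation does not answer the point either, because it depends on the fitted covariance being adequate.

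**Conclusion.** The concern holds in conditional form. The planned model does assume equal variance at the two occasions, and the missing-data approach relies on it. Its standard errors are right with complete follow-up or equal variances, too small if follow-ups are missing and the 8-week variance is larger, and too large if it is smaller. A larger 8-week variance is plausible for a sample entered through a screener, but it is not shown.

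The size is modest. At about 10% dropout, alpha is roughly 5.2% to 5.6% for the two widening cases tabulated. It passes 6% only when a clearly larger 8-week spread meets dropout of about 20% or more, or when dropout is around 35%. The precision gain applies whatever the dropout: about 3% of the pairwise SE (0.406/0.420) to 13% (0.369/0.426) in the two cases worked. All of this rests on assumed SDs, correlations and dropout unrelated to arm and outcome. Dropout that differs by arm could also bias the estimates, which is a separate matter. The change is worth making because it protects in either direction at almost no cost, not because the planned test has been shown to be invalid.

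**What to change.** Replace the primary model, and its re-use for secondary outcomes measured at baseline, with a two-occasion model that has:

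- time as a factor;
- an unstructured covariance, so that each occasion has its own variance;
- a baseline mean held common across arms.

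With `post` coded 0 at baseline and 1 at 8 weeks, and `time` as the occasion number, one form is `nlme::gls(phq8 ~ post + post:condition, correlation = corSymm(form = ~time|pid), weights = varIdent(form = ~1|time), na.action = na.omit)`. The three `post:condition` terms are the between-arm differences in change. Freeing the variance corrects the standard errors; the common baseline mean supplies the precision. This form keeps baseline-only participants in the analysis, as the Missing data section requires.

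Regressing 8-week PHQ-8 on condition and baseline PHQ-8 is a close alternative that needs no equal-variance assumption across occasions, but it drops participants without follow-up and so departs from that section.

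The cost is one extra variance parameter and a change of code. No new data are needed.

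### The secondary-analysis rule gives the immediate post-test data no prespecified analysis and cannot be fitted to any outcome that lacks a baseline

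*Combined protocol and SAP*

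**What the plan says.** The Protocol describes three occasions. At baseline, "they will first complete a questionnaire of demographics and well-being at baseline (roughly 4 minutes"). After randomisation participants "complete the post-test measures (roughly 4 minutes) just after the SSI and eight weeks later". The last part of the Protocol, just before the SAP, says that participants complete "questionnaires asking about their well-being and experiences with the interventions at baseline, post-test, and 8-week follow-up".

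The SAP contains one model form. Under Main analysis, PHQ-8 is regressed on condition, "measurement time point (1 = baseline, 2= 8-week follow-up), and the 2-way interaction between condition and measurement time point as IVs", with a random intercept per participant. Under Secondary analysis the rule is "Researchers will re-run the same analysis as above separately for each secondary outcome collected". The only other secondary analysis is the main analysis with covariates added.

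The SAP gives no other coding of time, no analysis for the immediate post-test, and no model for an outcome observed once. The secondary outcomes and their measurement times are not listed.

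**The concern.** The data collection has three waves and the analysis rule has two. The trial asks how long a single session should be, and the answers given directly after the session bear on that question. Under the stated rule they have no place in any model.

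The rule also presumes that every secondary outcome has a value before the intervention. Experience of an intervention cannot have one.

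In both cases an analyst must depart from the SAP, and the SAP does not say how. Which occasions to contrast, and with what model, would then be settled after the data are in hand.

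**Working it through.** **1. Is the immediate post-test a separate wave?** The Protocol's own durations are: screener and information 2 minutes, baseline 4, longest SSI 15, post-test 4. With another 4 for the same measures at 8 weeks, 2 + 4 + 15 + 4 + 4 = 29 minutes. This matches the Protocol's stated total, so the post-test is a wave in its own right.

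**2. What does the two-occasion rule use?** With 1,100 participants and an outcome measured at all three waves, there are 1,100 × 3 = 3,300 possible rows. Time coded as baseline or 8 weeks keeps 1,100 × 2 = 2,200. The 1,100 left out are the whole post-test wave. The planned design itself is sound for two occasions: 1 intercept + 1 time + 3 condition + 3 interaction = 8 columns, rank 8.

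**3. What happens without a baseline?**
- Measured after the SSI and at 8 weeks, or at 8 weeks only: the coding admits only the 8-week row. Time is constant, so its column is a multiple of the intercept and the three interaction columns are multiples of the condition columns. The matrix has 8 columns and rank 4. The interaction, which is the term under test, is not estimable.
- There are then 1,100 observations and 1,100 random-intercept levels, so the intercept variance cannot be separated from the residual variance.
- Measured just after the SSI only: no row is usable.
- Recoding time as post-test and 8 weeks would make the model fit, but the interaction would then compare change after the session, not the conditions' effect on the rating.

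**4. What would a baseline-adjusted comparison gain where a baseline exists?** Assume equal SDs σ at both occasions, complete data, n = 1,100 / 4 = 275 per arm and correlation r with baseline. The documents give no r, so 0.5 and 0.7 are assumptions. For a difference between two arms:
- change contrast: variance = 2 × 2σ²(1 − r)/n
- baseline-adjusted contrast: variance = 2 × σ²(1 − r²)/n
- ratio of standard errors = √[(1 − r²) / (2(1 − r))] = √[(1 + r)/2]

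| r | SE, change | SE, adjusted | Ratio |
|---|---|---|---|
| 0.5 | √(2/275) = 0.085σ | √(1.5/275) = 0.074σ | √0.75 = 0.87 |
| 0.7 | √(1.2/275) = 0.066σ | √(1.02/275) = 0.061σ | √0.85 = 0.92 |

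**The case against.** The best defence is that the same analysis can be read as the same model form at each outcome's own time points. An analyst could then re-run the two-occasion model as baseline against post-test. That model would be fittable, with only one pairwise correlation to represent. The defined question is PHQ-8 change to 8 weeks, and the documents state no hypothesis about an immediate effect. This stands in part: a reader might infer that the immediate effect will never be tested, and the documents do not support that. They show only that no such test is prespecified. The generous reading still leaves the choice of occasions open, and it does nothing for an outcome without a baseline.

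A second defence is that no such outcome is named. The Protocol sentence on questionnaires literally places experience items at all three waves, and those items may be descriptive acceptability data rather than secondary outcomes. This also stands. The inference rests on two facts: an intervention cannot be rated before it is received, and the Protocol describes the baseline questionnaire as demographics and well-being only. It is probable, not established.

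A reader might also infer that the plan's random-intercept model would give wrong standard errors across three waves, because answers minutes apart correlate more than answers 8 weeks apart. The documents propose no three-wave model, whether with numeric time or a three-level factor, so that criticism does not apply to this plan.

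**Conclusion.** The point holds as a gap in the secondary analyses. By the text alone, every immediate post-test observation is left out of analysis, and no test of the immediate effect of session length is prespecified. This part needs no assumption beyond reading the time coding as written.

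The second part is conditional. If any secondary outcome is measured only after the SSI, the stated model is not estimable for it (rank 4 of 8 columns, or no usable rows).

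The precision gain from the better method, a standard error 0.87 to 0.92 times that of the planned change contrast, rests on equal SDs, complete data and assumed correlations of 0.5 to 0.7. The primary PHQ-8 comparison from baseline to 8 weeks is unaffected, and no change in sample size follows.

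**What to change.** Replace the sentence under Secondary analysis with a table of secondary outcomes and their measurement times, and a rule by type:

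1. **Outcomes with a baseline.** Compare conditions separately at post-test (where measured) and at 8 weeks, each in a linear model adjusted for that outcome's baseline value. If one joint model is preferred, use time as a three-level factor with unstructured covariance and baseline means constrained equal across arms. The constraint matters. Without it, and with complete data, the condition contrast at an occasion is the raw difference between arms. Its standard error is then 1/√(1 − r²) times the adjusted one, which is 1/√0.51 = 1.40 at r = 0.7. The SAP should name one of the two approaches.
2. **Outcomes measured only after the SSI.** Compare conditions at that occasion in a linear model adjusted for baseline PHQ-8, with no time term and no random intercept. Data exclusion limits the analysis to people who completed baseline, so this covariate should be available.

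The cost is a few lines of SAP text and a little more analysis, with no new data. There are two downsides. The post-test contrasts add secondary tests; Inference criteria applies p < 0.05 to all analyses with no adjustment, so they must be counted in any multiplicity handling. Separate comparisons also use only participants observed at that occasion, whereas the joint model keeps everyone with any data, as the Missing data section intends.
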